### 13. Sample size

The main outcome considered for this study is the mean dose of norepinephrine at 72 hours after CRRT initiation. Previous studies consider that a difference of at least 0.10 micrograms/kg/min without changes in the MAP, in the intervention group compared to the control group, is a meaningful difference to detect.

Standard deviation for norepinephrine: 0.10 micrograms/kg/min.

Type of test: Two-tailed, with a confidence level of 95% and a statistical power of 80%. Solving the following equation to calculate the sample size using the comparison of 2 means method; a total of 34 patients, 17 within each group, is required. If a 10% loss is assumed, the final sample size will be 36 individuals, 18 in the intervention group (AN69 Oxiris membrane), and 18 in the control group (standard AN69 membrane).

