## 10. Goals

Primary goal: Change in norepinephrine requirement by at least 0.1 micrograms / kg / min to maintain similar MAP after initiation of CRRT with Oxiris membrane compared to standard AN69 membrane. MAP measurements will be performed hourly and norepinephrine requirement will be recorded at that time.

Exploratory goals:

- Effectiveness of the AN69-Oxiris membrane in reducing interleukin serum levels (IL 6, IL 10, and TNF alpha).

Serum will be taken every 8 hours for its measurement by ELISA method.

- To establish the safety (the same risk infection and bleeding) of using the AN69- Oxiris membrane in patients with AKI and COVID-19 infection who require CRRT.

Gross bleeding events (gastrointestinal or urinary) as well as catheter-associated infection events (criteria according to IDSA) will be recorded.

- Length of stay in UCI among patients who used AN69-Oxiris membrane in compared to the use of a conventional membrane (standard AN-69) in critically ill patients with COVID-19 associated AKI and CRRT requirement.

- To investigate the effect of AN69-Oxiris in reducing 28-day mortality in contrast compared with the effect of a conventional membrane in this population.

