#### 16. Statistical analysis

Descriptive statistics will be used with measures of central tendency and dispersion of the data according to their distribution. The distribution of the variables will be analyzed with the Kolmogorov-Smirnov "Z" test. For categorical variables, frequencies and percentages will be used. For continuous variables with normal distribution, the mean and standard deviation will be shown. In contrast, the median and interquartile range will be used for continuous variables with an abnormal distribution.

The Student's t-test will be used to compare continuous variables between the two groups, in case of a normal distribution. The Mann-Whitney U-test will be performed for groups with an abnormal distribution. The analysis of data inside the same group at different time intervals (baseline vs 72 h) will be carried out using the Student's t-test, Wilcoxon sum of ranks, or McNemar's test, as appropriate.

Multivariate analysis for mortality will be performed using Cox proportional hazards, adjusted for the baseline SOFA score. Statistical analysis and graphs will be obtained using SPSS 19.0 software (Chicago, IL) and Graphpad Prism 5 software (San Diego, Ca), respectively. A p-value <0.05 will be considered significant. An intention-to-treat analysis will be pursued.

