#### 19. Follow-up variables

- Laboratory tests obtained from the electronic medical records during the hospital admission.

- Time on mechanical ventilation.

- Time and dose of vasopressor.

- Length of ICU-stay.

- Days of hospital stay.

- Recovery of kidney function (defined as dialysis-free at 28, 60, and 90 days after discharge).

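### 36 patients cover a 5.6% loss, not the stated 10%; ICU deaths count as short stays; and the plan is silent on deaths before 72 hours

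*Combined protocol and SAP*

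**What the plan says.** **Sample size (Section 13).** The primary variable is defined thus: "The main outcome considered for this study is the mean dose of norepinephrine at 72 hours after CRRT initiation". The target difference and the SD are both 0.10 micrograms/kg/min, two-sided 5%, power 80%, giving 34 patients (17 per arm). Then: "If a 10% loss is assumed, the final sample size will be 36 individuals", that is, 18 per arm. Section 13 does not say whether a death counts as a loss.

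**Tests (Section 16).** "The Student's t-test will be used to compare continuous variables between the two groups, in case of a normal distribution". Otherwise: "The Mann-Whitney U-test will be performed for groups with an abnormal distribution". Mortality has a Cox model adjusted for baseline SOFA. On the analysis population there is one sentence: "An intention-to-treat analysis will be pursued".

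**ICU stay.** Section 10 (Goals) lists it as exploratory and Section 12 (Outcomes) as secondary. Section 19 (Follow-up variables) collects it as "Length of ICU-stay". None of these treats a death in ICU separately from a discharge.

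**Dose data.** Section 10 says: "MAP measurements will be performed hourly and norepinephrine requirement will be recorded at that time". Section 19 adds "Time and dose of vasopressor". Section 10 words the primary goal as a change in dose and Section 13 as the dose at 72 hours. Neither says what value is used for a patient who dies before 72 hours.

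**The concern.** The three points share a cause, patients who leave observation early, but they differ in weight.

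1. The stated loss allowance does not follow from the stated requirement. A reader who relies on it will think the trial keeps 80% power at 10% loss.
2. Length of ICU stay is an efficacy outcome on which shorter is better. A patient who dies in ICU on day 5 has a shorter stay than one discharged alive on day 15. With no separation of the two, an arm with more deaths can look better. The mortality analysis would show the imbalance but would not correct the ICU result.
3. The primary value is fixed at 72 hours in ventilated patients on vasopressors who need CRRT. With no rule for earlier deaths, the choice could be made after results are known, in an open-label trial of 36 patients.

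**Working it through.** **1. Loss allowance.** Inputs from Section 13: difference 0.10, SD 0.10 (d = 1), two-sided 5%, 34 required, 10% loss, 36 enrolled.

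- Reproducing 34: the two-sample t-test has df = 2n - 2 and noncentrality d x sqrt(n/2). With n = 17 the noncentrality is sqrt(8.5) = 2.92 and power is 80.7%. With n = 16 it is sqrt(8) = 2.83 and power is 78.1%. So 17 per arm is the smallest size reaching 80%, and the stated 34 is right.
- Inflating for loss: 34/(1 - 0.10) = 37.8, so 38. Multiplying instead, 34 x 1.10 = 37.4, also gives 38.
- What 36 covers: (36 - 34)/36 = 5.6%, two patients.
- At 10% loss: 36 x 0.9 = 32.4, or about 16 per arm, with power of about 78%.

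**2. ICU stay.** The documents give no mortality rate and no stay lengths. Assumed: mean stay 7-12 days for deaths and 14-20 for survivors, the same in both arms, so only mortality differs. The apparent advantage of the arm with more deaths is (difference in mortality) x (survivor stay - death stay).

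- 60% versus 40%: from 0.20 x (14 - 12) = 0.4 to 0.20 x (20 - 7) = 2.6 days shorter.
- 50% versus 40%: from 0.10 x 2 = 0.2 to 0.10 x 13 = 1.3 days shorter.

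In simulation (18 per arm, gamma stays, coefficient of variation 0.5-0.7), a false win is a significant result favouring the arm with more deaths, nominally 2.5%.

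| Assumed mortality | False wins, plain stay | ICU-free days, arm with more deaths |
|---|---|---|
| 50% vs 40% | 2.5-6% | 0.9-1.5 days fewer |
| 60% vs 40% | 3-13% | 1.9-3.0 days fewer |

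On ICU-free days to day 28 with death as zero, the difference points the right way and false wins are about 1% or less.

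**3. Death before 72 hours.** No plan figure can be checked. The calculations show only what different unstated rules would do, with 18 per arm, SD 0.10, no true effect, and assumed death rates and death-dose correlations of 0.3-1.

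| Assumed deaths | False wins, survivors only | False wins, last dose, half of deaths charted as zero |
|---|---|---|
| 10% vs 5% | 3-5% | 4% |
| 20% vs 10% | 3-7% | 6-7% |
| 30% vs 10% | 4-16% | 10-15% |

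- The 16% needs perfect correlation; at zero correlation there is no bias.
- If the last dose equals the unseen 72-hour dose, false wins under the last-dose rule are 2.3-2.6%.
- If doses rise by 0.10-0.20 before death in both arms, t-test power for a true 0.10 benefit under the last-dose rule falls to 54-76% at 10% deaths and 42-72% at 20%.
- Ranking deaths worst is safe against false wins (0.3-2.4%), but power is 60-72%, 41-58% and 27-42% at 10%, 20% and 30% deaths.

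**The case against.** **On the loss figure.** The normal approximation gives 2 x (1.96 + 0.84)^2 = 15.7, so 16 per arm and 32 in all. Since 32/0.9 = 35.6 rounds up to 36, 36 does cover 10% under that formula. Section 13's equation is missing from the available text, so this route cannot be ruled out. But Section 13 states 34, and 34, 10% and 36 do not agree. What stands is that the shortfall is one to two power points. A reader might infer a seriously underpowered trial; the figures do not support that.

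**On ICU stay.** The outcome is secondary at most and cannot change the primary conclusion. The mortality analysis would sit beside it, and the 13% lies at the edge of assumed ranges. All of that stands and limits the weight. It does not remove the fault, because the comparison itself still credits death.

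**On the primary endpoint.** A reader might infer that the plan compares survivors only and so biases the primary result. The documents do not say so. The intention-to-treat sentence and the recorded doses fit other rules equally well. Section 15 excludes a life expectancy under 72 hours, SOFA above 11 and age over 75, which should make early deaths fewer without excluding them. This objection stands: the demonstrated defect is silence, not bias.

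A reader might also infer that carrying the last dose forward is the evident remedy. It is not. It is sensitive to charted zeros and to doses that rise before death. A dose recorded as a patient dies may not be sustaining the similar MAP on which the outcome is conditioned. It also gives no value for a patient who never starts CRRT, which is possible because Section 11 randomises on the day of admission (Section 17 says before each CRRT treatment).

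**Conclusion.** The point holds in three parts of unequal weight.

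1. **Wrong as written, small.** On the stated 34, an enrolment of 36 allows for two losses (5.6%). At 10% loss, t-test power is about 78% instead of 80%. This rests only on Section 13's own figures.
2. **A cheap improvement to a secondary outcome.** The direction of the fault follows from Sections 12 and 16. Its size rests wholly on assumed mortality and stays, and it is slight when mortality differs little between arms.
3. **Clarification only.** The plan leaves open what an early death contributes to the primary comparison, whether that is read as the 72-hour dose or the change. The figures for particular rules depend on assumed death rates and correlations and are not estimates of bias in this plan.

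Together these should be fixed before analysis. None invalidates the trial.

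**What to change.** 1. **Section 13.** Keep 36. Either state the allowance as two patients (5.6%), or keep 10% and state power of about 78% (t-test, 16 per arm). Say whether loss includes deaths. Cost: one sentence.
2. **Sections 12 and 16, ICU stay.** Make the between-arm comparison one in which death cannot count as benefit, for example ICU-free days to day 28 with death as zero. Report plain stay descriptively, separately for survivors and deaths. ICU stay and 28-day mortality are already planned, so little or no new collection is needed. The cost is a changed estimand and lower power when mortality is equal. At an assumed 40% in both arms, with survivors staying 10 versus 20 days, t-test power is 26-42% for ICU-free days against 39-64% for plain stay; at 14 versus 20 days it is 11-18% against 13-24%.
3. **Sections 12 and 16, primary outcome.** Before results are known, fix a rule for deaths before 72 hours that is consistent with the intention-to-treat sentence, and apply it whether the dose or its change is analysed. Report these deaths by arm and add a sensitivity analysis that ranks them worst; its low power makes it unsuitable as the main analysis. The estimand (last dose, composite or rank) is the sponsor's choice. If last dose is chosen, define which hourly record counts and what applies to a patient who never starts CRRT. Cost: wording only, since hourly doses are already recorded.

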### 14. Inclusion criteria

1. Patients aged  $\geq 18$  years old.
2. A diagnosis of a confirmed, defined by a positive rt-PCR for SARS CoV-2, or suspected COVID-19 disease, with suggestive findings on a chest CT scan.
3. Patients on mechanical ventilation.
4. The presence of an informed consent signed by the next of kin.

5. Patients with KDIGO AKI stage 2: defined by a rise in creatinine 2-2.9 times baseline and/or a urinary output less than 0.5 ml/kg/hr for 12 hours, with failure after a furosemide stress test.
6. The use of vasopressor, any dose.
7. Complete medical history and complete laboratories.

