#### 12. Outcomes

Outcomes:

-Primary outcome: to establish the superiority of treatment with the AN69-Oxiris membrane to sustain a similar MAP with a lower requirement of norepinephrine (at least 0.1 micrograms/kg/min) after 72 hours of treatment initiation, in patients with COVID-19 associated AKI requiring CRRT, compared to the usage of a standard AN69 membrane.

-Secondary outcomes:

- To evaluate the effectiveness of the AN69-Oxiris membrane in reducing interleukin serum levels (IL 6, IL 10, and TNF alpha).
- To demonstrate the advantage of the AN69-Oxiris membrane in decreasing 28-day mortality from the start of CRRT.
- To establish the safety of using the AN69-Oxiris membrane in patients with AKI and COVID-19 infection who require CRRT.
- To examine the efficacy of the AN69-Oxiris membrane in reducing the length of ICU stay compared to the use of a conventional membrane (standard AN-69) in critically ill patients with COVID-19 associated AKI and CRRT requirement.

Variables:

Acute kidney injury. Elevation in serum creatinine or decrease in the urinary output according to what is established in the KDIGO guidelines.

Mean arterial pressure. MAP is considered as the perfusion pressure for organs and, a value greater than 60 mmHg is adequate to maintain perfused the organs of an average person. The mean arterial pressure will be registered, either obtained through a peripheral arterial line (calculated from the area under the curve of the arterial pressure graph) or the non-invasive monitor using the oscillometric method.

Furosemide stress test: This term refers to a furosemide bolus of 1 mg/kg (ideal body weight) with subsequent measurement of urine output after 2 hours. It is considered negative when the urine output during this interval is less than 200 ml.

Safety variables:

\* Clotting of the circuit: it is defined as the presence of clots in the circuit lines and/or filter, which condition rise in the transmembrane, pre-filter, or post-filter pressures, warranting a change of the filter.

\* Allergic reaction: the sudden presence of erythema or rash at any time after starting CRRT treatment.

\* Access bleeding: the occurrence of continuous bleeding at the vascular access insertion site any time after the start of CRRT treatment.

\* Catheter-related bloodstream infection: the presence of any microorganism in blood cultures drawn from catheter's lumen.

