#### 15. Exclusion criteria

1. Chronic kidney disease KDIGO stage 4, 5, or 5D.
2. Next of kin unwilling or patient unwilling to participate.
3. Patients with a life expectancy of fewer than 72 hours according to the attending physician criteria.
4. Patients older than 75 years.
5. Patients with SOFA > 11.
6. Patients with severe liver failure.

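### Entry on any vasopressor dose, with no expected control-arm dose stated, leaves it unshown that a 0.10 micrograms/kg/min difference at 72 hours is reachable, and entry dose is neither stratified nor adjusted for

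*Combined protocol and SAP*

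**What the plan says.** Section 14 (Inclusion criteria), item 6, requires "The use of vasopressor, any dose". It sets no lower limit and does not name the drug. Section 11 makes norepinephrine the first-line vasopressor, but a patient on another agent alone would still meet the wording of item 6.

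Section 12 defines the primary outcome as superiority in sustaining a similar MAP "with a lower requirement of norepinephrine (at least 0.1 micrograms/kg/min) after 72 hours of treatment initiation". Section 9 states the hypothesis in the same terms. Section 10 speaks of a change, still compared with the standard membrane: "Change in norepinephrine requirement by at least 0.1 micrograms / kg / min to maintain similar MAP after initiation of CRRT".

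Section 13 fixes what is powered: "The main outcome considered for this study is the mean dose of norepinephrine at 72 hours after CRRT initiation". The target is "a difference of at least 0.10 micrograms/kg/min without changes in the MAP, in the intervention group compared to the control group", and the spread is given as "Standard deviation for norepinephrine: 0.10 micrograms/kg/min". This leads to 17 per arm, and 18 after allowance for loss.

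Section 16 compares the groups by t-test, or by Mann-Whitney if a Kolmogorov-Smirnov check finds non-normality. The only covariate adjustment is for baseline SOFA in the mortality model. Sections 11 and 17 describe randomisation in Epidat and mention no stratification. No section gives an expected norepinephrine dose at entry, or in the control arm at 72 hours.

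**The concern.** The outcome has a hard lower limit and the entry criterion does not keep patients away from it. A patient who would be on 0.05 at 72 hours with the standard membrane can gain at most 0.05 from Oxiris, and a patient already weaned can gain nothing. If the control mean at 72 hours is below 0.10, the difference sought in Sections 9, 12 and 13 cannot occur, however well the membrane works. A working membrane could then give a difference well under 0.10 and be read as having missed its target.

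There is a second, smaller issue. Entry dose is likely to predict the 72-hour dose. With 18 per arm, and neither stratification nor adjustment, a chance imbalance at entry carries into the 72-hour comparison.

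**Working it through.** **Inputs from the plan (Sections 13 and 16).** Difference 0.10, SD 0.10, two-sided 5%, 80% power, 17 per arm (18 after loss), t-test or Mann-Whitney.

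**1. The plan's own figure.** The standardised difference is 0.10/0.10 = 1. The exact two-sample t-test needs 16.7 per arm, so 17. Power at 17 per arm is 80.7%. The stated sample size reproduces.

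**2. The bound.** Write C for the mean control dose at 72 hours and T for the mean Oxiris dose. Since T ≥ 0, C − T ≤ C. A difference of 0.10 needs C ≥ 0.10, and reaches it at C = 0.10 only if every Oxiris patient is off norepinephrine.

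**3. Size under an assumed dose distribution.** The documents give none, so this is a range. Assumptions: control doses are gamma-distributed with SD 0.10; the Oxiris dose is max(0, dose − 0.10); 17 per arm. The achieved mean difference is E[min(dose, 0.10)]. At a control mean of 0.10 the gamma is exponential, so this is 0.10 × (1 − e⁻¹) = 0.063. The rest is by simulation.

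| Control mean at 72 h | Achieved difference | t-test power | Mann-Whitney power |
|---|---|---|---|
| 0.20 | 0.096 | 79% | about 84% |
| 0.15 | 0.086 | 75% | about 87% |
| 0.10 | 0.063 | 58% | about 92% |

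At a control mean of 0.30 the floor has no visible effect (difference 0.100, t-test power about 81%).

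**4. Adding patients already weaned.** Assumptions: a fraction of patients would be at zero at 72 hours under the control membrane; the others are gamma with SD 0.10; the shift is floored as before; 18 per arm.

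| Mean among those still treated | Fraction at zero | Mann-Whitney power |
|---|---|---|
| 0.15 | 20% | about 64% |
| 0.15 | 30% | about 49% |
| 0.20 | 20% | about 51% |
| 0.20 | 30% | about 35% |

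The rank test is robust to the floor only while few control patients are tied at zero.

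**5. Chance imbalance.** If entry doses also had SD 0.10 (an assumption), the standard error of the between-arm difference in mean entry dose would be 0.10 × √(2/18) = 0.033, one third of the target. This does not bias the test, but it adds noise that stratification and adjustment would largely remove.

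**The case against.** A reader might infer that the floor prevents the trial from showing its effect. The documents do not support that, for four reasons.

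- The powered quantity is a difference between arms at 72 hours, not a fall of 0.10 in each patient. It can also arise if control doses stay high or rise. Admitting low-dose patients does not make them common.
- Missing a mean difference of 0.10 is not the same as missing significance. With 18 per arm and SD 0.10, an observed difference of 2.032 × 0.10 × √(2/18) = 0.068 is already significant.
- Section 16 moves to Mann-Whitney for non-normal data. If its Kolmogorov-Smirnov rule is applied in each arm, power in the 58% case is about 84%.
- Low doses may have a smaller SD. If the SD were half the mean, t-test power at control means of 0.05 to 0.10 (18 per arm) would be at least 99.9%, although the difference would be only 0.049 to 0.080.

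All of this stands, and it limits the point to what can happen. It does not remove it. The rank test loses its advantage once many patients are weaned, a significant rank test does not establish the 0.10 difference in Sections 9 and 12, and a smaller SD would mean the Section 13 input is wrong.

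A reader might also infer that the exclusion "Patients with SOFA > 11" pushes doses down. That cap is on a total score, and nothing in the documents ties it to norepinephrine dose.

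**Conclusion.** The point holds in a limited form. The bound is arithmetic and needs no assumption: the benefit in mean dose cannot exceed the control arm's 72-hour mean, and the plan does not show that this mean leaves room for 0.10. The cost in power does rest on assumptions. It runs from negligible (control mean about 0.20 or more, few patients weaned) to severe (control mean near 0.10 under the t-test, or 20–30% of patients at zero under the rank test), and the documents do not say where the trial lies. The lack of stratification or adjustment for entry dose is a separate, certain omission that is cheap to repair at this sample size.

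**What to change.** 1. Stratify the randomisation by entry norepinephrine dose, with a cut-point the sponsor sets from the expected distribution.
2. Make the primary 72-hour comparison in all randomised patients, adjusted for entry dose: for example ANCOVA, or a stratified rank test if doses are skewed. The dose is already to be recorded hourly (Section 10), and Section 16 already uses a baseline value. Define one time at which entry dose is taken, because Section 11 places randomisation on the day of admission and Section 17 before each CRRT treatment.
3. Report the difference by entry-dose stratum as supportive only. Making the higher-dose stratum the key estimate would cost power: about 65% with 12 per arm and about 51% with 9 per arm, even at the full 0.10 difference.
4. State the expected norepinephrine dose at entry and in the control arm at 72 hours, including the share expected to be at zero. Reconcile item 6 of Section 14 with the 0.10 difference and 0.10 SD in Section 13, and restate those figures if they do not fit.

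No entry dose is proposed. A minimum would be a clinical choice, and it would not stop patients from being weaned by 72 hours.

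The cost is one randomisation factor in Epidat and a little more analysis. No patients are lost.
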